Recently, magnetic resonance imaging (MRI) has become one of the most common and reliable diagnostic methods in medicine. The results of the still improving imaging performances, new functionalities, and more affordable prices represent a pronounced trend toward equipping hospitals and clinics with MRI scanners [1]. The rapid development of this technology has created the need to construct devices capable of monitoring vital signs of at-risk patients during MRI examinations. The risk group in the context of MRI includes neonatal, paediatric, disabled, anesthetised, and insensible patients [2]. The monitoring of life functions is also recommended for persons with implanted pacemakers, patients developing reactions to contrast media, and persons with mental disorders who may not be able to communicate with the system operator or to use the alarm button. However, efforts are being made to monitor at least some basic physiological parameters such as respiration and heart activity [3] during each MRI examination, regardless of the patient category.

Although MRI is a noninvasive method of investigation and does not expose patients to ionizing radiation, it has some psychological effects on patients. Some researchers [4],[5] have already demonstrated that 5 to 10% of patients undergoing MRI examinations experience severe claustrophobia or panic attacks during the scanning process, whereas 30% report milder distress and fear. Such increased stress stimuli and arousal may in turn lead to a phenomenon known as hyperventilation, which is increased ventilation of the lungs and significant acceleration and deepening of the breath, often resulting in fainting.

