Conventional monitoring equipment is not designed to work in the harsh MRI environment, distinguished by a magnetic induction of 1.5 T, 3.0 T, or even higher values and with radio frequency (RF) impulses of considerable electromagnetic (EM) field intensity [13]. The presence of metal or electronic components under such conditions can cause burns on the patient's skin and alter the EM field distribution and, thus, degrade the quality of imaging. Additionally, the signal transmitted using electrical conductive wires is vulnerable to the effects of a strong EM field, which complements the list of drawbacks of typical electronic measuring devices. On the other hand, optical sensors are fully penetrable in terms of the EM radiation applied in MRI, causing no interference. They are free from metal parts and function via optical fibres, resulting in their immunity to EM fields.

Study goals and objectives

The main objectives include:

1. Testing the sensor system with participation of MRI patients, where the result measures relate both to feasibility and health outcomes.
2. Verifying the signal quality, detecting RR and HR, and checking long-term measurement capabilities of the sensor system.
3. Analysing changes in RR and HR in the context of the system ability to detect a high level of stress, hyperventilation and other symptoms of claustrophobia in MRI patients.

Study Design

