The acquisition of physiological signals relies on placing the sensor mat under the patient's back during standard MRI procedures. Before and after the MRI scanning, the patient gets to complete the State Trait Anxiety Inventory (STAI) questionnaire. The part of the body that is being scanned and the time of the MRI examination are not relevant. Although an average MRI scanning lasts from 20 to 40 minutes, we assume that the study will be no longer than 1 hour as the administration of contrast media may prolong the survey. Up to 200 MRI patients of different age, weight and sex will be involved in the study. Exclusion criteria from the study are the same as exclusion criteria from MRI procedures. The sensor mat does not cause health changes in patients and the study is of observational type. The analysis will concern changes in RR and/or HR during MRI, with particular emphasis on the beginning and the end of the examination, i.e., 1- or 2-minute parts of the whole recording, as it shown in Fig. 1. The mean RR and/or HR values recorded at the beginning and the end of the MRI scanning will be referred to the STAI X-1 scores gathered before and after the MRI scanning, respectively. The research scheme includes also the collection of the STAI X-2 subscale before the MRI scanning.

[figure not shown]

Fig. 1. General scheme of the study.

Methodology

Fibre-optic sensor system

The sensor system consists of a sensor mat, an interrogation module and a laptop personal computer (PC). As shown in Fig. 2, the sensor mat includes a spring-board that converts body movements including lung- and heart-induced motions into strain, and a single fibre Bragg grating (FBG) or an FBG matrix bonded to the board measures this strain. The instantaneous spectral position of the FBG reflection peak can be calibrated in terms of the respiration and heart activity readings. Thus, the sensor also acquires ballistocardiographic (BCG) signals, and to operate effectively, the mat has to be placed between the back of the patient (as close to the heart as possible) and the mattress of the MRI track table.

[figure not shown]

Fig. 2. Sensor mat based on a (a) single FBG and (b) FBG matrix.

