MIAM is both a research institute and medical centre, where data management and information security are provided in accordance with the ISO IEC 27001 standard. A copy of the certificate is included as **Appendix A**.

Statistical Analysis Plan

Descriptive statistic methods will be used to evaluate the state anxiety and RR and/or HR indicators, as well as to assess the difference between the first and second anxiety measurement. A correlation analysis with the Pearson product-moment correlation coefficient will be performed to check if the initial RR and/or HR level is related to state anxiety measured right before the MRI study.

Since we hypothesise about the individual variability of the change in the RR and/or HR levels during an MRI session, a growth mixture model analysis [22] will be performed to statistically differentiate the subject groups according to the trends in repeated measures of RR and/or HR. After that, the analysis will be performed with the use of the Student's t-test to check whether the so-identified groups differ on the magnitude of change in the state anxiety observed during the study. An Alpha level of 0.05 will be used in all of the statistical tests.

The analysis will be performed using R statistical software version 3.4.0 [23]. The Growth mixture model analysis will be performed using the lcmm package version 1.7.7 [24]. The power analysis will be performed with the pwr package version 1.2-1 [25]. Plots will be created using the ggplot2 package version 2.2.1 [26].

Quality Assurance

MIAM has a quality management certificate based on the ISO 9001:2008 and AQAP 2120:2009 requirements. Copies of the certificates are included as **Appendix B**.

Expected Outcomes of the Study

Correlations between the STAI X-1 scores collected before and after the MRI scanning and the mean RR values recorded at the beginning and the end of the MRI scanning, respectively, are expected. Similarly, correlations between the STAI X-1 scores and the HR indicators should also be noticeable. We also expect the STAI X-2 scores will be useful in estimating the risk of anxiety symptoms during MRI.

At least two manuscripts, one containing the results of the STAI scores in relation to RR, and the other containing the results of the STAI and HR analysis, will be submitted for publication.

Dissemination of Results and Publication Policy

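### Student's t-test is named for comparing growth-mixture classes whose number and sizes the plan does not fix; Welch-type tests and a rule for one class or for three or more would close the gap

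*Combined protocol and SAP*

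**What the plan says.** The relevant text is the second paragraph of the Statistical Analysis Plan. The premise is a hypothesis about patients: "Since we hypothesise about the individual variability of the change in the RR and/or HR levels during an MRI session". On that basis, "a growth mixture model analysis [22] will be performed to statistically differentiate the subject groups according to the trends in repeated measures", the measures being RR and/or HR. The classes are then compared on change in the state anxiety score (STAI X-1, before to after the scan): "the analysis will be performed with the use of the Student's t-test to check whether the so-identified groups differ on the magnitude of change". One significance level covers everything: "An Alpha level of 0.05 will be used in all of the statistical tests".

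The section names the R version and the package for the mixture model. It does not give the number of classes, a rule for choosing it, the variance form of the t-test, or an analysis for one class or for three or more. Study Design sets only a ceiling on size: "Up to 200 MRI patients of different age, weight and sex will be involved in the study".

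**The concern.** A mixture model lets the data decide how many classes there are and how large each is. A t-test needs exactly two groups, and its pooled form needs equal variances unless the groups are of equal size. The plan joins the two methods without saying what happens when they do not fit.

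Two things are at stake. The first is the 5% level: with unequal classes and unequal spread, the pooled test can be far too liberal or far too strict. The second is whether the test exists at all. Objective 3 is "Analysing changes in RR and HR in the context of the system ability to detect a high level of stress" and related symptoms, and this comparison is the only planned test that sets change in RR or HR against change in anxiety. If the model returns one class, that question has no planned answer. If it returns three, the analyst must choose a method after seeing the data.

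**Working it through.** **No figure to reproduce.** The ceiling of 200 comes with no power, effect size, SD or class split, so it cannot be rebuilt. The only stated figure to test against is alpha 0.05.

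**Inputs**
- N = 200, the ceiling in Study Design. Alpha 0.05 from the Statistical Analysis Plan; two-sided is assumed.
- Smaller class of 10, 20 or 60, which is 5%, 10% or 30% of 200. These shares are borrowed from the Rationale, where "5 to 10% of patients undergoing MRI examinations experience severe claustrophobia or panic attacks during the scanning process, whereas 30% report milder distress" and fear. They are rates of reported distress, not of RR or HR classes, so they only suggest plausible sizes. Sizes of 40 and 100 are assumed.
- SD ratio r (smaller class over larger): 0.67, 1, 1.5 and 2, all assumed. The documents give no SD for change in X-1.
- Normal data, class membership taken as known, no true difference.

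**Formula.** Let the smaller class have size n1 and SD r, and the larger have size n2 and SD 1.
- True variance of the mean difference: V = r²/n1 + 1/n2.
- Variance the pooled test expects: P = [((n1−1)r² + (n2−1))/(N−2)] × (1/n1 + 1/n2).
- Type I error ≈ 2[1 − Φ(1.972/√(V/P))], where 1.972 is the critical value on 198 degrees of freedom.

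**Worked case, 160/40, r = 2.**
- V = 4/40 + 1/160 = 0.10625.
- P = [(39×4 + 159)/198] × (1/40 + 1/160) = 1.5909 × 0.03125 = 0.0497.
- √(V/P) = 1.462, and 1.972/1.462 = 1.349.
- 2[1 − Φ(1.349)] = 0.177. Simulation gives 0.178.

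**Equal classes, 100/100.** P = [(99r² + 99)/198] × (2/100) = (r² + 1)/100 = V for any r, so the level is held.

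**Simulated type I error of the pooled test (200,000 replicates)**

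| Split | r = 0.67 | r = 1 | r = 1.5 | r = 2 |
|---|---|---|---|---|
| 190/10 | 0.5% | 5% | 17% | 28% |
| 180/20 | 0.8% | 5% | 15% | 25% |
| 160/40 | 1.4% | 5% | 12% | 18% |
| 140/60 | 2.2% | 5% | 9% | 13% |
| 100/100 | 5% | 5% | 5% | 5% |

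Welch's test stays between 4.9% and 5.2% in every cell. The distortion needs both unequal sizes and unequal SDs, and it runs in both directions.

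**Number of classes.** This part needs no assumption.
- Two classes: the named test applies.
- Three or more: the named test does not apply. The plan gives no overall test, no contrasts and no adjustment.
- One class: there are no groups to compare.

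**Is there another test of change against change?** The Pearson correlation in the Statistical Analysis Plan relates the initial RR or HR level to pre-scan anxiety. Study Design and Expected Outcomes relate the mean at the start to the score before, and the mean at the end to the score after. All of these relate level to level. The class comparison stands alone.

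**The case against.** The plan never says pooled. It names R, whose t-test function uses the unequal-variance form unless told otherwise, so the analysis as run might already be Welch's. That is fair: if so, the variance part shrinks to a clarification. But the plan names Student's test and no option, and the gap on class number remains either way.

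The error rates also rest on assumed SD ratios and on class shares taken from distress rates. That stands too. They show what could happen, not what will.

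Objective 3 speaks of detecting high stress and does not name change in the STAI score. True, but the Statistical Analysis Plan itself chose that outcome for this test.

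A reader might infer four stronger things, none of which the documents support:
- That severe, milder and no distress imply three classes as readily as two. Nothing ties those groups to RR or HR trends.
- That the sponsor would run unadjusted pairwise t-tests. For three equal classes that would give about 11.5% familywise error, but the plan contains no such procedure.
- That treating assigned class as known invalidates the test. The documents give no class separation from which to judge this.
- That a regression on RR or HR change should replace the class comparison. The team chose classes because it expects patients to differ in how they change. When rising and falling classes were both given larger anxiety change, a linear slope test rejected in only about 3% to 5% of simulated studies, so it would miss that pattern.

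**Conclusion.** The point holds as a gap in specification; no stated figure is wrong. The class-number part follows from the text alone: one class leaves no test, and three or more leave none specified. The variance part is conditional on the pooled form being used and on class sizes and SDs both being unequal. Under the assumptions listed, type I error then lies between 9% and 28% when the smaller class is the more variable, and between 0.5% and about 2% when it has 0.67 times the SD. With equal class sizes the concern about variance disappears. The repair is cheap enough to be worth making without knowing which case will arise.

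**What to change.** Keep the class comparison as the main analysis and replace the t-test sentence with text to this effect:

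> The number of classes will be fixed by a stated criterion (for example, lowest BIC) before STAI data are linked. Change in X-1 will be compared between two classes by Welch's t-test, and between three or more by Welch's ANOVA followed by Holm-adjusted Welch contrasts. If one class is found, change in X-1 will be regressed on the patient's change in RR (separately, HR) from the start segment to the end segment, with HC3 standard errors.

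The regression is a fallback only. If Welch's version was already intended, say so by name.

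The cost is a few sentences and a little R code, with no new data. If SDs are in fact equal, Welch's test loses some power. At an assumed standardised difference of 0.5 and N=200, power falls from 80.4% to 79.5% at 160/40 (about 1 point), from 56.1% to 53.0% at 180/20 (3 points) and from 33.5% to 28.9% at 190/10 (5 points).

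Two limits remain. Welch's 5% is for normal data: with an assumed skewness of 1.5 it was about 8% at 190/10 and 6.5% at 180/20, so a very small class still calls for caution. The fallback assumes a linear relation.

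### The only test of RR/HR change against anxiety change goes through latent groups; a regression on the continuous change should be added beside it

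*Combined protocol and SAP*

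**What the plan says.** Objective 3 (Study goals and objectives) is "Analysing changes in RR and HR in the context of the system ability to detect a high level of stress", together with hyperventilation and other signs of claustrophobia. Study Design likewise makes change in RR and/or HR during the scan the subject of the analysis.

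The SAP names two tests that link the signals to anxiety:

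- A Pearson correlation to "check if the initial RR and/or HR level is related to state anxiety measured right before the MRI study". This is level against level, at the start only.
- A growth mixture model to "statistically differentiate the subject groups according to the trends in repeated measures of RR and/or HR", followed by a "Student's t-test to check whether the so-identified groups differ on the magnitude of change in the state anxiety observed during the study".

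The reason given for the second begins "Since we hypothesise about the individual variability of the change in the RR and/or HR levels during an MRI session". The number of classes and their expected sizes are not stated.

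The Project summary, Study Design and Expected Outcomes also relate the mean RR/HR in the opening window to the pre-scan X-1 score, and the mean in the closing window to the post-scan score. These comparisons are continuous, but again level against level.

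On size and error, the plan says "Up to 200 MRI patients of different age, weight and sex will be involved in the study", "An Alpha level of 0.05 will be used in all of the statistical tests" and "The power analysis will be performed with the pwr package version 1.2-1". It gives no effect size, target power or result.

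**The concern.** Both sides of the change question are measured on full scales: RR/HR change over the scan, and X-1 change from before to after. The SAP replaces the first with a class label before testing it. A patient just over a class boundary then counts the same as an extreme one, and variation within a class is ignored. This costs power under a graded relation even if class membership were known without error.

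The stated reason does not require groups, because variability between patients is equally compatible with a continuous spread of trends.

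Two things are at stake. A real graded relation could be missed with data that would have shown it on the full scale. And a difference between class means gives no estimate of X-1 points per unit of RR or HR change. That estimate bears more directly on whether the system tracks anxiety, and on the Project summary's aim of finding signal values that mark dangerous anxiety.

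**Working it through.** The plan has no power figure to reproduce.

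**Inputs.** From the documents: alpha 0.05 (two-sided assumed) and at most 200 patients. Assumed, because not given: correlation r between RR/HR change and X-1 change, 0.10 to 0.40; two classes (implied by a t-test); splits from 50:50 to 5:95.

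**Step 1. Graded relation, full-scale test (Fisher z).** Power ≈ Φ(atanh(r)·√(n−3) − 1.960).
For n=200 and r=0.20: 0.2027 × √197 = 2.845; 2.845 − 1.960 = 0.885; power 81.2%.
For r=0.25: 0.2554 × √197 = 3.585; power 94.8%.

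**Step 2. Graded relation, two known groups.** Cutting a normal trend into shares p and 1−p multiplies r by k = φ(z_p)/√(p(1−p)). This gives k = 0.798 at 50:50, 0.734 at 25:75 and 0.585 at 10:90. The information kept is k²: 64%, 54% and 34%. Power comes from the noncentral t with noncentrality √n·rk/√(1−(rk)²).
At r=0.20 and 50:50: rk = 0.160, noncentrality 2.286, power 62.4%.
At r=0.20 and 10:90: rk = 0.117, noncentrality 1.666, power 38.1%.

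| n, r | Full scale | 50:50 | 25:75 | 10:90 | Loss (points) |
|---|---|---|---|---|---|
| 200, 0.20 | 81.2% | 62.4% | 55.1% | 38.1% | 18.8 / 26.1 / 43.1 |
| 200, 0.25 | 94.8% | 81.7% | 74.8% | 54.8% | 13.1 / 20.0 / 40.0 |
| 100, 0.25 | 71.1% | 52.2% | 45.6% | 31.0% | 18.9 / 25.5 / 40.1 |

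At n=200 and r=0.20 to 0.25 the loss is therefore 13.1 to 43.1 points. Over wider inputs it runs from 0.3 (n=200, r=0.40, 50:50) to 56.7 (n=100, r=0.30, 5:95).

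**Step 3. Graded relation, groups estimated.** A two-component normal mixture fitted to one change value per patient served as a simplified stand-in for lcmm (n=200). With r=0.15 to 0.30 (600 runs), the loss was about 10 to 26 points for normal trends, 12 to 24 for skewed trends, and under 1 to 7 for clearly bimodal trends. Other 400-run simulations at r=0.20 gave 83% full scale against 54% and 42% for normal trends (losses of 29 and 41) and 48% for skewed trends (35). These figures vary too much between runs to carry the conclusion; Step 2 carries it.

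**Step 4. The opposite case: a true class alone drives X-1 change.** Same stand-in, n=200, correlation 0.20 between class and X-1 change, 400 runs. Full-scale test against class t-test:

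| True class share | 3 SD apart | 4 SD apart |
|---|---|---|
| 5% | 32% v 50% | 46% v 69% |
| 7.5% | 41% v 56% | 54% v 77% |
| 10% | 49% v 63% | 56% v 72% |
| 20% | 58% v 66% | 64% v 73% |

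At 2 SD the two tests are about equal (42% v 40% for a 20% class). Allowing for variation between runs, the full-scale test loses roughly 6 to 11 points for a 20% class (one run gave 4) and about 10 to 28 points for a class of 5 to 10%.

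**The case against.** The strongest reply is that the study aims to find a subgroup. The Rationale cites severe claustrophobia or panic in 5 to 10% of patients and milder distress in 30%, and it stresses early identification of those likely to panic. Objective 3 concerns a high level of stress. Latent trajectory classes can suit that aim, and Step 4 shows the class t-test ahead when a small, distinct class exists. This stands, and it rules out demoting the class test as if that were free.

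A reader might infer that the documents describe a proportional rise of RR/HR with anxiety. They do not. The Project summary says anxiety usually raises RR, with hyperventilation at the extreme, which fits either a gradient or tiers. The linear relation in Steps 1 to 3 is an assumption of this review.

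It is also fair that the initial-level Pearson test is not the only continuous comparison, since Expected Outcomes anticipates correlations at both times. These do not fill the gap. The covariance of two changes also depends on how start RR/HR relates to post-scan X-1 and how end RR/HR relates to pre-scan X-1, and the plan examines neither.

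Finally, the mixture model uses the trend over the scan, whereas a start-to-end difference can miss a surge that settles before the end. That stands too, and is a reason to keep both analyses.

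**Conclusion.** The gap is real: no planned analysis relates continuous RR/HR change to continuous X-1 change, although change is the subject of Objective 3. Under a linear relation with normal trends, known groups, n=200 and two-sided 0.05, the class t-test gives up about 13 to 43 points of power at r=0.20 to 0.25 for splits from 50:50 to 10:90.

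It would be tempting to read that range as a property of the plan. It is not, because r, the class number, the class shares and the final sample size are all unstated, and the loss spans under 1 to about 57 points over wider inputs. Nor do the documents support the reading that grouping is wrong in itself: with classes 3 to 4 SD apart it is the stronger test. Since the plan gives no ground for choosing between a continuous spread and distinct classes, it should not rest Objective 3 on the grouped test alone. This is an inexpensive improvement to the analysis, not a flaw that invalidates the study.

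**What to change.** Keep the growth mixture model and the class t-test. Beside them, pre-specify in the SAP a linear regression of X-1 change (post-scan minus pre-scan) on each patient's RR change, and a separate one on HR change, each reporting the slope with a 95% CI. Define RR or HR change as the closing-window mean minus the opening-window mean from Study Design. That section allows windows of 1 or 2 minutes, so name one length in advance.

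The cost is SAP wording and one model per signal on data already planned, with no new patients or procedures. There are two downsides. It adds one test per signal; the SAP now says only that 0.05 applies to every test, so these should be counted in any statement on multiplicity. And the start-to-end difference does not capture a mid-scan surge, which the class model may still describe.

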A schematic of the research setup is shown in Fig. 3. The sensor mat is placed in the MRI chamber underneath the chest area of the patient to ensure proximity to the heart and lungs. A few meters optical fibre is threaded through a wall opening and connected via a fibre-optic for angled physical contact (FC/APC) -type connector to an FBG interrogation module in the operation room. To interrogate the sensor mat, a commercially available DL-BP1-1501A broadband light source by *DenseLight Semiconductors* [14] with I-MON 256/512 USB monitor by *Ibsen Photonics A/S* [15], or sm130-700 integrated unit by *Micron Optics* [16] will be used. The data from the interrogation module is sent via an USB or Ethernet interface

to the laptop PC with software developed for signal visualisation, data archiving as well as automatic determination of RR and HR.

[figure not shown]

Fig. 3. Research setup.

MRI scanner

Achieva 1.5T by *Philips* [17] or Discovery MR750w 3.0T by *General Electric* [18] MRI scanners will be used in the study.

STAI

In order to measure anxiety in patients undergoing MRI procedures, the Polish version of the STAI by Spielberger et al. [19] was used. The inventory is designed to measure the level of anxiety as a current state in response to a given situation (the X-1 subscale) as well as a relatively stable personal trait (the X-2 subscale). Evaluation of anxiety level in patients will be conducted according to a repeated measurement protocol. The subjects will complete the STAI X-1 subscale twice, i.e., just before entering the MRI scanner and immediately after leaving the scanner. The STAI X-2 subscale will be completed before the MRI scanning. As a result, the level of experienced anxiety before and after the MRI scanning, as well as the level of anxiety as a constant personality trait in patients, will be obtained.

Safety Considerations

The presence of the sensor mat during the MRI examination does not pose a threat to the patient. Because the sensor mat is free from metal elements, it is fully penetrable by the EM radiation used in MRI and causes no interference. We have previously showed that the fibre-optic sensor is transparent to the MRI system and does not introduce any artefacts into the spin echo (SE) T1 weighted and T2 weighted or to the gradient echo (GE) T2 weighted imaging sequences [20],[21].

Follow-Up

No recommendations other than for standard MRI procedures.

Data Management

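### The anxiety t-test treats growth-mixture classes as known groups, so it does not estimate the difference between the latent classes, and the direction of the error depends on within-class correlation

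*Combined protocol and SAP*

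**What the plan says.** In the Statistical Analysis Plan section, a growth mixture model "will be performed to statistically differentiate the subject groups according to the trends in repeated measures of RR and/or HR". The next step is a "t-test to check whether the so-identified groups differ on the magnitude of change in the state anxiety observed during the study". The error rate is set for every test: "An Alpha level of 0.05 will be used in all of the statistical tests". Software is named: "The Growth mixture model analysis will be performed using the lcmm package version 1.7.7".

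The outcome comes from the STAI description under Methodology: "The subjects will complete the STAI X-1 subscale twice", once before and once after the scan. X-1 is not named as part of the class model. On numbers, Study Design says: "Up to 200 MRI patients of different age, weight and sex will be involved in the study".

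The documents do not give the rule for assigning patients to classes, the number of classes, any measure of classification quality (entropy, mean posterior probability), or any step that allows for misclassification. They give no expected class separation, no SD for X-1 change, and no confidence interval for this comparison.

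**The concern.** A growth mixture model does not observe class membership. A patient with a 55% probability of one class and a patient with a 99% probability enter the t-test alike, as full members. Some patients in each assigned group belong to the other latent class, so the difference between assigned groups is not the difference between latent classes.

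This is the only significance test in the SAP that links change in RR/HR during the scan to change in state anxiety, and so it bears directly on the third objective. The planned Pearson correlation covers only the initial RR/HR level against pre-scan anxiety. Study Design puts its emphasis on one- or two-minute segments at the two ends of the recording. If only those segments feed the model, well-separated classes cannot be taken for granted. A real link could be understated or missed. Equally, an association that runs through RR/HR itself could be reported as a difference between patient types.

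**Working it through.** The plan states no effect size, power or separation, so there is no figure to reproduce. What follows is illustration.

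**Inputs.** From the documents: N = 200 (the stated maximum) and alpha 0.05 (two-sided assumed). Assumed: two classes whose RR/HR trend scores are normal and D SDs apart; SD of X-1 change 10 points; true class difference d = 5 points (0.5 SD) unless stated; each patient assigned to the more probable class; within-class correlation rho between RR/HR trend and X-1 change.

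**1. Shrinkage when rho = 0.** The expected assigned-group difference is d × f, where f = P(truly 1 | assigned 1) + P(truly 2 | assigned 2) − 1. With equal classes, each probability is Φ(D/2):

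| D | Φ(D/2) | f = 2Φ(D/2) − 1 | Expected difference (true value 5) |
|---|---|---|---|
| 2 | 0.841 | 0.683 | 3.41 |
| 3 | 0.933 | 0.866 | 4.33 |
| 4 | 0.977 | 0.954 | 4.77 |

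With a 20% class, f is almost the same: 0.684, 0.858 and 0.949.

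**2. Power when rho = 0.** With known equal classes, SE = 10 × √(1/100 + 1/100) = 1.414, and power = Φ(5/1.414 − 1.96) = Φ(1.58) = 94%. Multiplying 5 by f gives about 68% (D = 2), 87% (D = 3) and 92% (D = 4). Simulations that estimated the classes gave 63%, 85% and 91%. With a 20% class, where the assigned small group also shrinks, power goes from 81% with known classes to 43%, 66% and 76%.

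**3. Standard error and error rate when rho = 0.** In the same simulations (N = 200, up to 400 runs per setting), at D = 2 with equal classes the mean t-test SE was 1.51 and the actual SD of the assigned-group difference was 1.57. With no true difference, rejection was between 2.5% and 6.3% across settings. The t-test is therefore sound for the groups it compares. Read as an interval for the latent-class difference, its limits covered 5 points in 81% of runs at D = 2, 92% at D = 3 and 96% at D = 4. Part of that shortfall is mis-centring and part is width: the misclassification-corrected estimate had an SD of about 2.3 at D = 2.

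**4. When rho is not zero.** With equal classes, assignment also selects on the within-class part of the trend, which adds rho × SD × 4φ(D/2). At D = 2, φ(1) = 0.242, so the expected difference is 3.41 + rho × 10 × 0.968:

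- rho = 0.1: 3.41 + 0.97 = 4.38
- rho = 0.2: 3.41 + 1.94 = 5.35
- rho = 0.3: 3.41 + 2.90 = 6.32

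With no class difference at all and rho = 0.3, the expected difference is still 2.90 points. A large-sample simulation agreed to within 0.03. Shrinkage of a 5-point difference is exactly offset at rho = 5(1 − f)/(10 × 4φ(D/2)):

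- D = 2: 1.59/9.68 = 0.16
- D = 3: 0.67/5.18 = 0.13
- D = 4: 0.23/2.16 = 0.11

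**5. The correction under both conditions.** With a 20% class, known class parameters, rho = 0 and a true difference of 1.0 SD (1,500 runs per setting):

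| D | t-test estimate (coverage) | Regression on posterior probability (coverage) |
|---|---|---|
| 2 | 0.68 (64%) | 1.00 (95%) |
| 3 | 0.86 (89%) | 1.00 (96%) |
| 4 | 0.95 (94%) | 1.00 (96%) |

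For a 0.5 SD difference at D = 2, power rose from about 41% to 49%.

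With the same 20% class at D = 2 and a true difference of 0.5 SD, within-class correlation changes the picture. At rho = 0.2 the t-test gives 0.57 and the regression 0.92; at rho = 0.3 they give 0.68 and 1.13. With no class difference and N = 200, rejection at rho = 0.2 was 21% for the t-test and 40% for the regression. At rho = 0.3 it was 42% and 71%.

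**The case against.** **The plan asks only about the groups it identifies.** For that question the assigned-group contrast is legitimate, with an adequate SE and null error rate (working, step 3). This stands. It does not help once the result is described as a difference between types of patient, which is the purpose of fitting latent classes.

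**The documents do not support a fixed direction.** A reader might infer that the result must be biased towards no difference. That requires X-1 change to be unrelated to RR/HR trend within class. The Expected Outcomes section anticipates correlations between X-1 scores and both RR and HR, and the Project summary says that anxiety usually raises RR. Neither establishes a within-class correlation of changes, but both make it plausible. This stands.

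**No confidence limits are planned.** A reader might infer that the plan reports limits that are too narrow. It states only tests at 0.05. Under-coverage arises only if someone reads a t-test interval as applying to the latent classes. This stands.

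**The obvious replacement can be worse.** Step 5 shows the posterior-probability regression overstating the difference when rho is 0.2 or more. A bias-adjusted three-step (BCH) analysis rests on the same independence assumption. This stands, and it rules out simply replacing the t-test.

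**The size is unknown.** Separation, class share and SD are all assumed here, and at 4 SD with rho = 0 little is lost. This also stands, but the plan asks nobody to report how well the classes separate, so a reader of the results could not tell which case applied.

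**Conclusion.** The point holds in a conditional form. The SAP classifies and then tests, and nothing carries classification uncertainty into inference about the latent classes.

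If X-1 change is independent of RR/HR trend within class, the test recovers about 0.7 of the latent-class difference at 2 SD separation, 0.85 at 3 SD and 0.95 at 4 SD, with a matching loss of power. If the two are positively correlated within class, a coefficient of about 0.11 to 0.16 is enough to cancel the shrinkage of a 0.5 SD difference with equal classes. Larger values reverse it and can produce an apparent class difference where none exists.

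These figures rest on two normal classes and most-probable-class assignment. Separation and correlation are assumptions, because the documents give neither. The documents do not show that the bias runs towards the null, that any stated interval is wrong, or that a posterior-probability analysis alone would put things right. The change is worth making because the effect can be large, its size cannot be judged in advance, and the fitted model already supplies what is needed.

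**What to change.** Amend the t-test sentence in the Statistical Analysis Plan section so that it:

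1. States the assignment rule, and reports entropy and the mean posterior probability per class.
2. Reports, beside the t-test on assigned classes, a regression of X-1 change on the k − 1 posterior class probabilities (for k classes) with robust or bootstrap standard errors, or a bias-adjusted three-step analysis. The regression also covers a solution with more than two classes, which a single t-test does not.
3. Checks within-class independence by adding each patient's observed RR/HR change to that regression, or by fitting a joint model of RR/HR and X-1 change.
4. Says that a class difference will be interpreted as such only if these analyses agree.

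On item 3, the coefficient of the observed RR/HR change is the check. In the two-class model used above, with trend score x (within-class SD 1) and posterior probability p, the expected X-1 change given x is, up to a constant, d × p + rho × SD × (x − D × p). The coefficient of p in the extended model is therefore d − rho × SD × D, the class difference at a given RR/HR change, and should not be reported as the overall class difference. Because p is computed from x, the two are strongly related. The check will be imprecise, and a non-significant coefficient does not prove independence.

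The cost is a few SAP sentences and a few lines of R, with no new data. The price is a wider interval for the class difference, and a weaker conclusion if the classes separate poorly or the assumption fails.
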